STUDY DURATION	
Study duration for each participating patient in the main study will be up to 15 months in total as follows:
 
Screening period: up to 8 wks.
 
If the patient's screening process is delayed as described above, extra time will be added to the duration of the screening period, but not in excess of an additional 4 wks (total of 12 wks screening period).
 
Treatment period: 12 months.
 
The LT-OLE study will continue until marketing approval.
 
Follow-up: during the main study one month post dosing for those withdrawn or not continuing on in the LT-OLE, and one month post EOS/ET in the LT-OLE.

NUMBER OF PATIENTS	Approximately 220 pre-pubertal boys and girls not yet 12 and 11 years of age, respectively, will be included and randomized 1:1 to the weekly MOD-4023 arm or the daily Genotropin ® comparator arm. Eligible patients that complete the main study will be allowed to continue in the LT-OLE.

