Effective Date: Date of final electronic approval

- Parameters of lipid metabolism (overnight fasting cholesterol, triglycerides, HDL, LDL, Lp(a), FFA).
- For males that are 13 years and older: LH, FSH and testosterone. For females that are 12 years and older: LH, FSH and estradiol.
- Fundoscopy (ONLY if there are signs or symptoms indicative of increased intracranial hypertension).
- Bone age.
- MOD-4023 serum levels.
- ECG.
- Return of used and unused injection devices and diary cards.
- Anti-MOD-4023 Abs.

Patients will be required to visit the study site for assessment of biochemical markers on day 4 (-1) post-dose. If a visit is performed on a dosing day, collection of MOD-4023 serum levels and anti-Mod-4023 Ab levels must be obtained pre-dose. For End of Treatment during LT-OLE Year 1, the ECG will be conducted at 7-12 hours post-dose and patients will be requested to inject MOD-4023 during the day/night at their convenience and come to the study site at the requested timepoint for the ECG. An ECG must still be obtained even if patients do not take the final dose. Visits may be split to allow for pre-dose blood collection for serum levels and antibody tests and post-dose ECG or the patient will be asked to come to the study site for blood collection, administer the required dose, and return to the study site 7-12 hours post-dose. For ET from LT-OLE Year 2 onwards ECG can be conducted without a timeframe requirement i.e. at any time, although the date and time that each is performed will be recorded.

Patients will be contacted by telephone 30 days [ $\pm$  5 days] after EOS/ET visit in order to obtain safety related information.

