b Hematology: RBC Count; HGB; HCT; MCH; MCHC; MCV; WBC Count and Differential; Platelet Count, PT/INR, PTT (if indicated only).

c Chemistry: total protein, albumin, total bilirubin; ALT, AST, GGT, LDH, CPK, alkaline phosphatase; sodium, potassium, calcium, phosphate; BUN, LFT, creatinine.

j Urinalysis: pH, glucose, ketones, erythrocytes, leukocytes, protein.

k Glucose metabolism: overnight fasting glucose and insulin; HbA1c.

l Lipid profile: overnight fasting cholesterol, LDL, triglycerides, HDL and FFA; Lp(a)

m For male patients that are at the age of 13 years and above.

n For female patients that are at the age of 12 years and above.

Effective Date: Date of final electronic approval

Study Procedure	LT-OLE – Year 2 until study closure				EOS/ET b	Follow-up a 30 days (±5) following EOS/ET
	Study Day (± in dy/s)	Study Wk (± in wk/s)	Study Month	Study Visit		
	117 (±2)	130 (±2)	143 (±2)	156 (±4)		
	27	30	33	36		
	17, 21...	18, 22...	19, 23...	20, 24...		
Auxology measurements c	X	X	X	X	X	
Physical examination and vital signs d	X	X	X	X	X	
ECG				X e	X e	
Pubertal status (Tanner stages)				X	X	
Urine pregnancy test for girls reporting 1 st menstrual cycle	X	X	X	X	X	
BA (Greulich-Pyle method using central BA reader)				X	X	
Dispense study drug	X	X	X	X		
Individual dose adjustment	X	X	X	X		
Diary card return	X	X	X	X	X	
Local tolerability	X	X	X	X	X	X
AEs	X	X	X	X	X	X
Prior & concomitant medications	X	X	X	X	X	X
MOD-4023 IP return	X	X	X	X	X	
Fundoscopy	ONLY if there are signs or symptoms indicative of benign intracranial hypertension					
Laboratory Assessments						
Hematology f , chemistry g , & urinalysis h		X		X	X	
IGF-1, IGF-1 SDS, IGFBP-3, and IGFBP-3 SDS		X		X	X	
MOD-4023 serum levels		X		X	X	

a Phone interview only.

b Pre- and post- dose assessments may be performed on separate days that will be appropriately recorded in the EDC.

c Actual Ht (mean of three consecutive measurements per patient per visit) measured on a calibrated wall mounted stadiometer.

d Body weight, ideally fasted in the morning, without shoes and having removed all outwear and heavy pocket items.

e ECG will be conducted at 7-12 hours post-dose for ET during year 1. ECG can be conducted at any time for ET from year 2 until EOS.

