3.5. Safety Endpoints

3.5.1. Adverse Events

The AE including time of the onset, severity, action/treatment and outcome of the AE resolution, related to somatrogon treatment or not, will be collected at each scheduled visit with the visit window specified in the Schedule of Activities in the protocol.

An AE is considered as a treatment-emergent adverse event (TEAE) if the event started on or after the first dose of somatrogon in the OLE period of the study. The AE reporting period

for this study will be defined as the duration from the first dose of somatrogan in the study until 28 calendar days following the final visit dose. AE with partial dates will be assessed using the available date information to determine treatment-emergent status; AEs with missing onset date/time will be considered as TEAE. AEs with missing resolve date/time will be considered as ongoing.

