Appendix 2. Data Derivation Details

Appendix 2.1. Definition and Use of Visit Windows in Reporting

Annual ADA characterization will be performed based on the algorithm below using visit windows as applied to ADPC dataset.

Period	From	To
Main	Day 2 (main dosing +1)	Day 410
OLE Year 1	Day 2/OLE Baseline (OLE dosing +1)	Day 410 (OLE Month 12)
OLE Year 2	Day 411	Day 774
OLE Year 3	Day 775	Day 1138
OLE Year 4	Day 1139	Day 1502

The following table will provide the adverse events reporting period to a given study period.

Period	From	To	AE linking to study period
Main	On or post first Main dosing date/time (in exposure dataset)	Prior to the first OLE dosing date/time	If the new AE strictly starts between the start and end dates of a given period, it will be counted in that period.
OLE Year 1 (visit13 -16)	On or post first OLE dosing date/time (defined in exposure dataset)	Visit 16 end date; if Visit 16 is missing, then first OLE dosing date + 365	
OLE Year 2 (visit 17-20)	“OLE Year 1 To” date + 1	Visit 20 end date; if Visit 20 is missing, then “OLE Year 2 From” date + 365	
OLE Year 3 (visit 21-24)	“OLE Year 2 To” date + 1	Visit 24 end date; if Visit 24 is missing, then “OLE Year 3 From” date + 365	
OLE Year 4 (visit 25-28)	“OLE Year 3 To” date + 1	Visit 28 end date; if Visit 28 is missing, then “OLE Year 4 From” date + 365	

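### SAP adverse-event windows do not match the protocol's follow-up call or their own table bounds, so collected events can fall outside the tables

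*SAP*

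**What the plan says.** **End of AE reporting.** SAP Section 3.5.1 (Adverse Events) starts the AE reporting period at the first somatrogon dose in the study and continues it "until 28 calendar days following the final visit dose". The term for that last dose is not defined. The same section calls an event treatment-emergent if it began on or after the first somatrogon dose in the OLE, and sets no end date. SAP Section 6.5.1 builds the incidence tables on TEAEs and lists all AEs.

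**Follow-up contact.** Protocol Section 5.4 states "Patients will be contacted by telephone 30 days", with a window of ±5 days, "after EOS/ET visit in order to obtain safety related information". The LT-OLE schedule in Protocol Appendix A heads this contact "30 days (±5) following EOS/ET" and marks AEs, local tolerability and concomitant medications for collection there. The synopsis (Study Duration) gives follow-up as "one month post EOS/ET in the LT-OLE". On the timing of the EOS/ET visit, Section 5.4 says: "Patients will be required to visit the study site for assessment of biochemical markers on day 4 (-1) post-dose". It also allows for a visit on a dosing day and for patients who do not take the final dose.

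**Assignment to study year.** SAP Appendix 2.1 says: "If the new AE strictly starts between the start and end dates of a given period, it will be counted in that period". In the same table, OLE Year 1 runs from "On or post first OLE dosing date/time (defined in exposure dataset", the main period ends before that dose, and each later year begins the day after the previous year's To date. The last row, OLE Year 4, ends at the Visit 28 end date, or 365 days after its From date if Visit 28 is missing.

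**The concern.** The two documents close the safety window differently. The SAP counts 28 days from a dose; the protocol counts 30 (±5) days from a visit that usually follows a dose by some days. An event first reported at the call can thus have an onset after the SAP's reporting period has ended. The contact exists to pick up post-treatment events, so those are the ones affected.

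The second rule contradicts itself. A strict inequality at both ends does not fit a table whose first OLE row opens on or after the dose and whose later rows follow one another without a gap. If a programmer takes the word literally, AEs starting on the first or last date of an OLE year enter no by-year count. One of those dates is the first OLE dosing day, when children switching from Genotropin have local tolerability assessed on site (Protocol Section 5.3).

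**Working it through.** The plan gives no figure of its own to reproduce here. Both checks are counts of days.

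**1. Reporting limit against follow-up contact**

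Inputs:
- contact on day 25, 30 or 35 after EOS/ET (earliest, nominal, latest; Protocol Section 5.4 and Appendix A);
- EOS/ET visit 0, 3 or 4 days after the last dose (Protocol Section 5.4; the glossary defines day 4 (-1) as day 3 or 4);
- reporting limit of day 28 (SAP Section 3.5.1), taking its undefined anchor to be the last dose.

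Days from last dose to contact = contact day + days from dose to visit. Days past the limit = that sum − 28.

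| EOS/ET visit | Last dose to contact: earliest / nominal / latest | Days past day 28 |
|---|---|---|
| on a dosing day, dose taken | 25 / 30 / 35 | −3 / 2 / 7 |
| day 3 after dose | 28 / 33 / 38 | 0 / 5 / 10 |
| day 4 after dose | 29 / 34 / 39 | 1 / 6 / 11 |

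The nominal contact is 2 to 6 days past the limit and the latest is 11 days past it. A contact early in its window can fall on or before day 28. Each weekly dose omitted before the visit adds 7 days.

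**2. Year-assignment rule**

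Inputs: four OLE years as in SAP Appendix 2.1, each taken as From to From + 365, with the next From = previous To + 1.

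- Length of each year, both ends included: 366 days. Total: 4 × 366 = 1464 days.
- From < onset < To: both end dates of each year are unassigned, 4 × 2 = 8 days; 8 / 1464 = 0.5%.
- From ≤ onset < To: 4 × 1 = 4 days unassigned.
- From ≤ onset ≤ To: 0 days unassigned.

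Only inclusive bounds cover every day.

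The first OLE dosing day needs separate treatment, because its bound is a date and time. Protocol Section 7.1 asks for AE times as well as dates. A reaction timed after the dose is strictly later than the bound and counts in Year 1. That day is therefore lost only when a date alone is recorded or used; with times, 8 − 1 = 7 days remain unassigned.

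**3. After the last row**

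The LT-OLE continues until marketing approval (SAP Section 2.2), so it is not limited to four years. Inclusive bounds do not help an AE with onset after the Year 4 To date: no row exists for it, including AEs reported at the follow-up contact after Visit 28.

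**The case against.** The strongest reply is that no loss is shown. The TEAE definition has no end bound, the SOC and PT tables are built on TEAEs, every AE is listed, and nowhere does the SAP exclude onsets after day 28. That stands. A reader might infer that the SAP discards every AE after day 28; the text does not support this. What remains is that Section 3.5.1 gives two windows that are not equivalent and does not say which governs the tables. If the reporting period acts as a filter, late events go; if it does not, it has no stated function. A listing does not replace an incidence table.

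A second reply is that 'strictly' may only mean that the onset itself, not a carried-over event, must fall in the period, and that contiguous rows imply inclusive bounds. That is probably the intent, but the sentence does not say so.

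A reader might also infer that injection-site reactions on the first OLE dosing day are lost. The date/time bound prevents that wherever a time is recorded and used. Nor do the documents make safety the main purpose of the extension: SAP Section 2.1 names efficacy, safety and immunogenicity together, and Protocol Section 8.6.5 puts annual HV and the other auxological and biochemical measures first.

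**Conclusion.** Both rules are wrong as written, at a minor level. The 28-day limit differs from the protocol's contact in length and anchor. The contact falls about 25 to 39 days after the last dose, nominally 30 to 34, and later if dosing stopped before the visit. This assumes that the SAP's undefined term means the last dose. AEs are lost from the tables only if the reporting period is applied as a filter, which the SAP neither states nor rules out.

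The year-assignment rule contradicts its own table. On a literal, date-only reading it leaves 8 of 1464 days (0.5%) in no year. This affects by-year counts, not TEAE status.

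It is tempting to turn the gap into a number of lost events. The documents give neither the number of children reaching follow-up nor an AE rate, so no such figure is supported, and the point does not need one.

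**What to change.** In SAP Section 3.5.1, end the AE reporting period at the protocol's follow-up contact, or at the end of its window, 35 days after EOS/ET, if no contact is made. This removes the undefined dose anchor. State whether the period limits the TEAE tables, and use the same end date for the person-year incidence rates in Section 6.5.1.

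In SAP Appendix 2.1, replace the 'strictly' wording with From ≤ onset ≤ To. Keep the date/time bound at the first OLE dose and say how an AE on that day is assigned when only a date is recorded. Add a row for AEs after the Visit 28 end date, covering follow-up and any later OLE year.

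The cost is a few lines of SAP text and matching programming. No visit, procedure or data collection changes. AE counts may rise slightly.

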3.5.2. Laboratory Data

Laboratory data will be collected according to the Schedule of Activities in the protocol, including hematology, chemistry, lipid profile, glucose metabolism, endocrinology and urinalysis lab tests.

3.5.3. Vital Signs

Vital sign data will be collected according to the Schedule of Activities in the protocol, including systolic blood pressure, diastolic blood pressure, heart rate, respiratory rate, temperature. Any clinically significant (CS) findings will be reported as an AE.

3.5.4. Antibodies

Blood samples for anti-drug antibodies (ADA) will be collected according to the Schedule of Activities in the protocol, including the ADA status (positive, negative, not done or not available) for the following items:

- Anti-human GH (hGH) antibodies
 - neutralizing
 - non-neutralizing
- Anti-somatrogan antibodies
 - neutralizing
 - non-neutralizing

ADA titer will be classified as 0 (i.e., ADA negative), 10, 50, 250, 1250, 6250. Titer values >6250 are reported as 6250.

ADA positivity will be defined as:

- Tested positive after the receipt of drug during the study (either in main period or OLE), if main period baseline was tested negative or titer as 0;
- Post-baseline titer > 4x main period baseline titer, if main period baseline was tested positive.

Otherwise, it will be classified as ADA negative.

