	
fasting cholesterol, triglycerides, high density lipoprotein (HDL), low density lipoprotein (LDL), lipoprotein a (Lp(a)), Free Fatty Acids (FFA).
 
 
• For males that are 13 years and older: Luteinizing Hormone (LH), Follicle-Stimulating Hormone (FSH) and testosterone. For females that are 12 years and older: LH, FSH and estradiol (Visit 8 only).
 
• Assessment of anti-MOD-4023 Ab (MOD-4023 arm) at Visits 2, 3, 4, 5, 6a, 7, 8a.
 
• Assessment of anti-hGH Ab (Genotropin® arm) at Visits 2, 4, 5, 6, 7 and 8 only.
 
• BA assessments at Visits 1, 2 (at Visit 2 only if historical data was provided for eligibility evaluation and not performed as part of Visit 1) and Visit 8 only.
 
• Fundoscopy (if there are signs or symptoms indicative of benign intracranial hypertension).
 
• ECG at Visit 2 for all patients, pre- dosing and ECG on Visit 6 for patients treated with daily Genotropin®. All MOD-4023 patients will undergo an ECG during Visit 6b, 7-12 hours post dosing.
 
• USA Only - The Participant Assessment Tool (PAT) completed at Wks 1, 2, 3, 4, 5 and 6 for MOD-4023 treated patients. In any given wk a new PAT will be completed for each PEN used that wk (in some cases more than 1 PEN may be used for full dose administration, in which case a PAT will be completed for each PEN used that wk. In some cases, more than 1 injection from the same PEN may be needed, in which case only 1 PAT is completed for that PEN that wk).
 
• USA Only - The Observer Assessment Tool (OAT) completed at Wk 1 for MOD-4023 treated patients. A new OAT will be completed for each PEN used (in some cases more than 1 PEN may be used for full dose administration, in which case an OAT will be completed for each PEN used. In some cases, more than 1 injection from the same PEN may be needed, in which case only 1 OAT is completed for that PEN). Wk 1 corresponds to study Visit 2, which will be at the site.
 
• Individual dose adjustment every three months based on weight.
 
• Drug dispensing Visits 2, 4, 5, 6, 7 and 8 (for patients entering the LT-OLE).
 
• QoL questionnaire (Visits 2 and 8 only); patients below the age of 7 and 0 days will be completing the questionnaire with their parents/legal guardians using a parent questionnaire while patients above and including the age of 7 and 0 days will be encouraged to use the child questionnaire. The QoL questionnaire will be completed in specific countries (determined by availability of validated translated tools) as described in Appendix L.
 
 
For MOD-4023 patients arm only, Visit 3 (Day 10 [+4 days] post first dose), Visits 6a (Month 6/Wk 26 [<math>\pm</math>3 wks]) and Visit 8a (Month 12/Wk 52 [<math>\pm</math>1 wk]) will be conducted on dosing day, blood samples will be taken pre-dose for assessment of MOD-4023 serum levels. These blood samples can be collected at site OR at patient's home, based on local regulations and nurse availability. If home visit, a questionnaire as described in Appendix I should be completed.
 
For Genotropin® patients on Day 10 (+4 day) post first dose a phone interview will be conducted according to the questions as provided in Appendix I.

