### 5.2.1 Visit 2 (Day 1/Baseline) – recommended injection days as indicated in [Appendix E](#)

Visit 2 must be conducted within 2 wks of randomization.

The following assessments will be conducted on Day 1/Baseline:

a 1. Western Europe, Israel, Australia, New Zealand, Canada and USA; 2. Central and Eastern Europe, Greece, Turkey, Latin America and Asia except for India and Vietnam 3. India and Vietnam.

b All visits, except Visit 3, can be conducted within the specified window to accommodate patient availability, but must be conducted on day 4 (-1) post dose.

c Applicable only for MOD-4023, Visit 3 assessments, if conducted on Day 14 (dosing day), should be done prior to dosing.

Effective Date: Date of final electronic approval

- Auxology measurements: Actual Ht (mean of three consecutive measurements) measured on a calibrated wall mounted stadiometer.
- AEs, local tolerability (aligned with Appendix H), and concomitant medications.
- Overall health status assessment, including complete physical examination and vital signs.
- Safety laboratory tests: chemistry, hematology and urinalysis.
- Pubertal status (according to Tanner stages).
- Assessment of thyroid function and biochemical markers: TSH, FT4, IGF-1, IGF-1 SDS, IGFBP-3 and IGFBP-3 SDS serum levels.
- Assessment of MOD-4023 serum levels (applicable for MOD-4023 arm only).
- Parameters of glucose metabolism: overnight fasting glucose, overnight fasting insulin, HbA1c.
- Parameters of lipid metabolism: overnight fasting cholesterol, triglycerides, HDL, LDL, Lp(a), FFA.
- Assessment of anti-MOD 4023 and anti-hGH Ab (depending on arm of study).
- BAa.
- ECG pre-dosing.
- Training for patients, parents or legal guardians on drug administration.
- Fundoscopy (if there are signs or symptoms indicative of benign intracranial hypertension).
- Training for patients, parents or caregiver for completing the PAT assessment.
- Administration of study drug at the study site by patient or parent/caregiver.
- MOD-4023 on-site OAT assessment (USA only).
- MOD-4023 on-site PAT assessment (USA only).
- QoL Questionnaire completion (in specific countries as indicated in [Appendix L](#)).
- Drug dispensing and accountability.

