### 5.2.3 Visit 3 (Day 10 [+4 days] post first dose) for Genotropin arm onlya

- Phone interview and questionnaire completion as provided in [Appendix I](#).
- AEs and local tolerability (aligned with Appendix H) assessment.
- Concomitant medication recording aligned with the questionnaire in [Appendix I](#).

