### 5.2.4 Visit 4 (Month 1/Wk 4 [+1wk])

The following assessments will be conducted at Visit 4 on Day 4 (-1) post dose:

- AEs, local tolerability, and concomitant medications.
- Overall health status assessment, including complete physical examination and vital signs.
- Safety laboratory tests: chemistry, hematology and urinalysis.
- Assessment of biochemical markers: IGF-1, IGF-1 SDS, IGFBP-3 and IGFBP-3 SDS serum levels.
- MOD-4023 serum levels (applicable for MOD-4023 arm only).
- Fundoscopy (ONLY if there are signs or symptoms indicative of benign intracranial hypertension).
- Anti-MOD-4023 Abs (MOD-4023 arm only).
- Anti-hGH Abs (Genotropin® arm).
- Return of used and unused injection devices to the site, diary card and PAT forms (USA patients only).
- Drug dispensing and accountability.

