3.4. Baseline Variables

Baseline is defined as the main period baseline for efficacy and biomarker assessment. Except the reference visit for AHV, is defined in Section 3.1 as the values at the previous 12 month in the OLE period.

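### ADA rules in the SAP: the Main window overlaps OLE Year 1 for switchers, and no rule is stated for a switcher without a main-period anti-somatrogon baseline

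*SAP*

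**What the plan says.** **Positivity rule (SAP 3.5.4).** There are two routes. A positive test after drug counts "if main period baseline was tested negative or titer as 0". A post-baseline titer more than four times the main-period baseline titer counts if that baseline was positive. Then: "Otherwise, it will be classified as ADA negative". The section also lists what is collected, "ADA status (positive, negative, not done or not available", but does not say when the last two categories apply.

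**Baseline and missing data.** SAP 3.4: "Baseline is defined as the main period baseline for efficacy and biomarker assessment". Its only exception is the reference visit for height velocity. SAP 5.3 sends missing safety data to a sponsor rulebook that is not among the documents; its named examples are dates and adverse event severity.

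**Windows (SAP Appendix 2.1).** The ADA table runs Main from Day 2 to Day 410, and OLE Year 1 from the day after OLE dosing to OLE Day 410. The adverse event table in the same appendix closes Main before the first OLE dose.

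**Sampling (Protocol).** The Synopsis lists "Assessment of anti-MOD-4023 Ab (MOD-4023 arm) at Visits 2, 3, 4, 5, 6a, 7, 8a". Section 5.2.1 (Visit 2) has "Assessment of anti-MOD 4023 and anti-hGH Ab (depending on arm of study". Section 5.8.9 limits the assay to the MOD-4023 arm during the main study. Section 5.2.5 gives both arms a sample at Visit 8. The Appendix A row for MOD-4023 antibodies marks Visit 2 with no arm label.

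**The concern.** Immunogenicity is part of the LT-OLE objective (SAP 2.1). Efficacy may be shown by ADA status and titer (SAP 6.1.1), and antibody frequencies by year and visit if the data are adequate (SAP 6.2.1).

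Patients switching from Genotropin meet somatrogon for the first time at OLE entry, so the boundary between Main and OLE is where their exposure begins. Two things look wrong there. A fixed Main end lets samples taken on somatrogon count in a period when these patients received Genotropin. And a positivity rule tied to a main-period baseline may have nothing to work with in the group whose seroconversion the extension is best placed to describe. In that case the default is negative, not unknown: reported incidence would be too low, and the ADA-negative efficacy subgroup would contain antibody-positive patients.

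**Working it through.** **Windows.** Main-study Day 1 is the first main dose, so Week 52 is Day 1 + 364 = 365, and its one-week window is Days 358 to 372 (Protocol 5.2.5). Let D be the main-study day of the first OLE dose. A switcher starts at least one day after stopping Genotropin, with a two-week allowance (Protocol Synopsis and 5.3). Without delay, D is earliest at 358 (last Genotropin dose the evening before an early Visit 8) and latest at 372 + 1 + 14 = 387.

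The plan's own bounds reproduce: 410 + 364k for k = 0 to 3 gives 410, 774, 1138, 1502. OLE Years 1 to 4 therefore meet without overlap; only the join between Main and OLE Year 1 overlaps.

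Shared days run from D + 1 to 410, a count of 410 − D. Visit 11 is 10 to 14 days after the first OLE dose; Visit 12 is nominally at +28.

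| D | Overlap (days) | Visit 11 | Nominal Visit 12 |
|---|---|---|---|
| 358 | 52 | 368–372 | 386 |
| 365 | 45 | 375–379 | 393 |
| 372 | 38 | 382–386 | 400 |
| 387 | 23 | 397–401 | 415, outside Main |
| 405 | 5 | 415–419, outside Main | 433, outside Main |
| 410 or later | 0 | outside Main | outside Main |

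Visit 11 lies wholly inside Main when D + 14 ≤ 410, that is D ≤ 396. Nominal Visit 12 does so when D ≤ 382. Later starts are permitted: Protocol 5.3 allows delayed entry up to 90 days after Visit 8, and longer for technical reasons.

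Patients continuing on somatrogon are hardly affected. They skip Visit 11, have Visit 12 by telephone, and reach Visit 13 at the earliest on Day 456 − 14 = 442. A Visit 8a sample could fall in the overlap, but the drug is the same on both sides.

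**Was there a Visit 2 sample in the Genotropin arm?**

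- Against: the Synopsis, 5.2.1 and 5.8.9, as above. The Appendix A row has seven marks (Visits 2, 3, 4, 5, 6a, 7, 8a/10), the same seven as the serum-level row that footnote bb limits to the MOD-4023 arm. For five of them (3, 4, 5, 6a, 7) body text limits the sample to that arm. For example, 5.2.4 has "Anti-MOD-4023 Abs (MOD-4023 arm only", and Visit 3 in the Genotropin arm is "Phone interview and questionnaire completion as provided in" Appendix I.
- For: the Visit 2 mark has no arm label, the neighbouring r-hGH antibody rows do have one, and SAP 3.5.4 takes its sampling from the schedule.

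The first reading is better supported but not certain.

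**Was there a sample just before the switch?** The main support is the Visit 8 line in 5.2.5. The Synopsis and 5.3 call a repeated sample the Genotropin group's baseline, but only for patients off treatment more than 90 days. In Appendix A the mark stands in the 8a/10 column: footnote d makes this Visit 10 for patients who continue, while footnote c limits 8a to the MOD-4023 arm.

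**Literal classification.** A switcher with no main-period baseline and a positive OLE sample fails the first route (no negative baseline), fails the second (no positive baseline), and falls to negative.

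**Size.** Let f be the fraction of switchers who default to negative for want of a baseline, and p the true seroconversion rate in switchers. With half the extension population switchers, the misclassified share is 0.5 × f × p. The half, f and p are all assumptions.

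| f | p = 5% | 10% | 20% | 50% |
|---|---|---|---|---|
| 0 | 0 | 0 | 0 | 0 |
| 0.5 | 1.25% | 2.5% | 5% | 12.5% |
| 1 | 2.5% | 5% | 10% | 25% |

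If p is also equal in both groups, reported over true pooled incidence is 1 − 0.5f: 100%, 75% and 50% for f = 0, 0.5 and 1.

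**The case against.** **The baseline problem may not arise.** On the unlabelled Appendix A row, switchers were sampled at Visit 2. SAP 3.5.4 counts positives from either period, so post-switch positives were evidently meant to count. The section has a not-available status, SAP 5.3 defers to a rulebook that we cannot see, and the ADA table shells in SAP Appendix 6 are redacted, so a separate category may exist. The SAP also cites a protocol Amendment V5.0 dated 2 May 2018, while the protocol at hand is labelled Amendment 2, 27 April 2018; nothing shows whether they are the same text. All this stands, and it makes the baseline point conditional. It does not answer it: the stated rule sends every unmatched case to negative, and no text sends a missing baseline elsewhere.

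**The proposed baseline sample is itself uncertain.** This also stands. Routine sampling of switchers at Visit 8 rests mainly on one line in 5.2.5, and 5.8.9 and footnote c point the other way.

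**Windows.** The analysis dataset might carry a period flag that settles the overlap. SAP Appendix 3 describes none, and the ADA table gives no tie-break.

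**Stronger readings to avoid.** A reader might infer that every switcher's Visit 11 sample falls in Main. The delayed-entry provisions rule that out. A reader might also infer that switchers' antibody incidence will be lost, or the pooled rate halved. Half is the extreme case f = 1 under equal seroconversion, and the documents give neither quantity.

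**Conclusion.** The window overlap is firm. It is 45 days for a Day 365 start, 23 to 52 days for undelayed switchers, and zero from Day 410. For first OLE doses up to Day 396, switchers' Visit 11 samples on somatrogon also count in their Genotropin period. Ever-positive status does not change; the annual attribution does.

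The baseline point holds with moderate confidence and only conditionally. It needs switchers to lack a Visit 2 anti-somatrogon sample, and both the not-available status and the external rulebook to leave the default in place. Its size cannot be taken from the documents and is zero if f = 0.

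Both effects are descriptive. The OLE has no hypothesis test (SAP 5.1), and the main-study comparison is untouched. Severity is minor to moderate.

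**What to change.** 1. End the Main ADA window at the earlier of Day 410 and the day of the first OLE dose, keeping that day's pre-dose sample in Main. The overlap is then zero for any start, in line with the adverse event table.
2. Define the anti-somatrogon baseline as the last sample before the first somatrogon dose: Visit 2 for the original somatrogon arm, Visit 8/10 or its repeat for switchers. Tie it to the dose and not to the window: a repeat more than 90 days after a Day 365 Visit 8 falls after Day 455, beyond the Main window.
3. Report patients without such a sample as not evaluable, with their number, and not as negative.
4. Reconcile the Synopsis, 5.2.5, 5.8.9 and Appendix A (the antibody row and footnotes c and d) on anti-MOD-4023 sampling in the Genotropin arm.

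The cost is SAP wording, derivation code, a protocol clarification and a count of samples already taken. The downside is real: if the Visit 8 sample was often not taken, many switchers become not evaluable and the ADA denominator shrinks.
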